5.2.4. Preparation, Handling, and Storage

Staff at each clinical study center or the healthcare professional will be responsible for preparation of lumasiran doses, according to procedures detailed in the Pharmacy Manual. In cases where lumasiran is administered at home by a caregiver, dosing may be prepared and administered by the caregiver according to procedures detailed in the Patient/Caregiver Storage and Administration Instructions. No special procedures for the safe handling of study drug are required.

Study drug will be stored upright and refrigerated at approximately [5±3°C].

A Sponsor representative or designee will be permitted, upon request, to audit the supplies, storage, dispensing procedures, and records.

Instructions specific to unused study drug and additional storage will be provided in the Pharmacy Manual and Patient/Caregiver Storage and Administration Instructions.

5.2.5. Packaging and Labeling

All packaging, labeling, and production of study drug will be in compliance with current Good Manufacturing Practice specifications, as well as applicable local regulations. Study drug labels and external packaging will include all appropriate information as per local labeling requirements. Additional details will be available in the Pharmacy Manual.

5.2.6. Accountability

The Investigator or designee will maintain accurate records of receipt and the condition of the study drug supplied for this study, including dates of receipt. In addition, accurate records will be kept of when and how much study drug is dispensed and administered to each patient in the study. Any reasons for departure from the protocol dispensing regimen must also be recorded.

At the completion of the study, there will be a final reconciliation of all study drugs. Used, partially used, and unused study drug will be returned to the Sponsor (or designee) or destroyed at the clinical study center according to applicable regulations.

Further instructions about drug accountability will be detailed in the Pharmacy Manual.

5.3. Concomitant Medications and Procedures

Use of concomitant medications and procedures will be recorded on the patient's CRF as specified in the Schedules of Assessments (see Table 1, Table 2, Table 3, and Table 4). This includes all prescription medications, vaccines, herbal preparations, over the counter medications, vitamins, and minerals. Any changes in medications or dialysis regimen during the study must be recorded on the CRF. Patients should not start new medication regimens during the study, including regimens of vitamins or herbal medication, without consultation with the Investigator.

If patients use nonsteroidal anti-inflammatory drugs intermittently or chronically, they must have been able to tolerate them with no previous side effects (eg, gastric distress or bleeding).

Standard vitamins and topical medications are permitted. However, topical steroids must not be applied anywhere near the injection site(s) unless medically indicated.

If taking pyridoxine (vitamin B6) for the treatment of PH1, patients must have been on a stable regimen for at least 90 days before screening and remain on this stable regimen during the screening period and through at least the Month 6 visit. Dose adjustments for interval weight gain are permitted. Patients should avoid high dose vitamin C preparations within 4 days prior to oxalate assessments.

Patients may be treated for PH1 according to local standard of care and dialysis maintenance as determined by treating physician. Patients should continue their current standard of care and dialysis regimen, including hyperhydration, crystallization inhibitors, and/or pyridoxine therapy at least until the Month 6 visit. Changes in dialysis regimen may be permitted only if medically indicated. Standard of care treatment may be adjusted after Month 6 in accordance with clinical judgement. If pyridoxine therapy is discontinued, pyridoxine levels should be assessed for at least the next 2 timepoints indicated in the Schedules of Assessments (see Table 1, Table 2, Table 3, and Table 4). Consultation with the Medical Monitor is required if treated with any new emerging products.

For other permitted concomitant medications administered subcutaneously, do not administer in same injection site area as the study drug, for at least 7 days after the last dose of study drug.

Any concomitant medication that is required for the patient's welfare may be administered by the Investigator. However, it is the responsibility of the Investigator to ensure that details regarding the medication are recorded on the CRF. Concomitant medication will be coded using an internationally recognized and accepted coding dictionary.

5.4. Treatment Compliance

Compliance with study drug administration will be verified by study staff.

5.5. Other Requirements

5.5.1. Contraception

Females of child-bearing potential must be willing to use a highly effective method of contraception from 14 days before first dose, throughout study participation, and for 90 days after last dose administration or until study completion. Pediatric/adolescent female patients must initiate one of the birth control methods below, which includes true abstinence, at menarche or must discontinue study drug.

Birth control methods which are considered highly effective include:

- Placement of an intrauterine device.
- Placement of an intrauterine hormone-releasing system.
- Bilateral tubal occlusion.
- Surgical sterilization of male partner (with the appropriate post-vasectomy documentation of the absence of sperm in the ejaculate; for female patients on the study, the vasectomized male partner should be the sole partner for that patient).
- Established use of oral (except low-dose gestagens), implantable, injectable, or transdermal hormonal methods of contraception.

- True sexual abstinence, when in line with the preferred and usual lifestyle of the patient. Periodic abstinence (eg, calendar, ovulation, symptothermal, post-ovulation methods) and withdrawal are not acceptable methods of contraception. Abstinent patients must agree to use one of the above-mentioned contraceptive methods if they start heterosexual relationships during the study and for up to 90 days after the last dose of study drug.

Investigators should advise females of childbearing potential of the most appropriate birth control method available within their country taking into account local medical practice.

Females of child-bearing potential include female patients who have experienced menarche (or begin menarche over the course of the study), and who are not postmenopausal or permanently sterilized (eg, bilateral tubal occlusion, hysterectomy, or bilateral salpingectomy). A postmenopausal state is defined as the absence of menses for 12 months without an alternative medical cause, confirmed by follicle stimulating hormone level within the postmenopausal range.

For male patients, no contraception is required. However, use by adolescent males of contraception (condom) may be required in some countries, eg, France, in order to comply with local requirements as described in the corresponding patient informed consent forms. Males with partners of child-bearing potential must agree to use a condom throughout study participation and for 90 days after the last dose of study drug or until study completion.

Compliance with contraception requirements will be assessed on a regular basis by the Investigator throughout the course of the study. The Investigator will ensure that adolescent patients, and their legal representatives if applicable, are adequately informed about contraceptive requirements and the need for contraception once a patient initiates heterosexual intercourse. The need for contraception and compliance with contraception requirements will be assessed at every visit for adolescent patients, and pregnancy testing will be performed before every dose for postmenarcheal females throughout the course of the study (see Section 6.5.5.2).

5.5.2. Dietary Restrictions

Patients should refrain from consumption of foods with high oxalate content, including, but not limited to, chocolate, rhubarb, spinach, and beet root, for 1 week prior to assessments of urinary and plasma oxalate.

6. STUDY ASSESSMENTS

The schedules of study assessments are provided in Table 1, Table 2, Table 3, and Table 4. Additional information on the collection of study assessments will be detailed in the Study Manual.

Urine collection assessments are not required for patients who are anuric (ie, produce <100 ml per day).

Where applicable country and local regulations and infrastructure for home healthcare allow, home healthcare may take place at a location other than the clinical trial site to perform study assessments, which may include collection of blood and urine samples, measurement of vital

signs, length/height and weight, an abbreviated physical examination/body system assessment, and preparation and administration of study drug (at the discretion of the Investigator).

6.1. Screening Assessments

The Investigator will notify the Sponsor before screening patients to allow an assessment of the ability of the site or any new trial participant to comply with the protocol given COVID-19 limitations.

An informed consent form (ICF) or assent form in the case of patients under the age of legal consent that has been approved by the appropriate Institutional Review Board (IRB)/Independent Ethics Committee (IEC) must be signed by the patient (or legal guardian if under the age of legal consent) before the Screening procedures are initiated. All patients (or their legal guardians if under the age of legal consent) will be given a copy of the signed and dated ICF and/or assent form. In the case when a patient reaches the legal age of consent during the study, the Investigator must obtain the patient's informed consent, and assent if applicable, prior to performing any further study interventions and/or procedures involving that patient (see Section 8.1.1).

Patients will be screened to ensure that they meet all the inclusion criteria and none of the exclusion criteria (see Section 4.1 and Section 4.2). Rescreening of patients is permitted with consultation of the Medical Monitor (see Section 6.1.2).

Patient demographic data and medical history/disease history will be obtained. Non-serious events occurring after signing of the ICF and prior to study drug administration will be captured as medical history. Any changes to medical history occurring between the screening assessment and Day 1 will be updated prior to study drug administration.

A blood sample for *AGXT* mutation analysis will be collected during Screening for patients who do not have documented PH1 genetic analysis to confirm eligibility.

For all patients who are not anuric, single-void urine samples (in triplicate) will be collected during screening to establish baseline. Also, in patients who are able to produce urine, 24-hour collections will be performed during Screening to establish baseline urinary oxalate levels (Section 6.1.2).

The timing of samples collected during Screening for plasma oxalate and plasma glycolate will be as shown in Figure 1.

The three most recent screening plasma oxalate samples collected prior to Day 1, which may include the pre-dialysis sample from the plasma oxalate profile collection for Cohort B patients, will be used to assess eligibility. If all 3 plasma oxalate assessments are obtained >60 days prior to Day 1, one additional plasma oxalate will be performed (at least 7 days prior to Day 1).

For subjects in Cohort B, there must be 2 separate plasma oxalate profile assessments performed during Screening, performed at least 1 week apart.

[figure not shown]
If a patient's stable dialysis regimen at the time of consent is interrupted during screening for ≤14 days, plasma oxalate levels should not be collected until the prior dialysis regimen has resumed for at least 2 weeks. If a patient's stable dialysis regimen at the time of consent is

interrupted for >14 days, plasma oxalate should not be collected until the stable dialysis regimen has resumed for at least 4 weeks.

If a patient's stable dialysis regimen at the time of consent is permanently changed during screening, plasma oxalate should not be collected until the new dialysis regimen has been established for at least 4 weeks. Any plasma oxalate profiles and pre-dialysis plasma oxalate samples collected prior to this point will not be used for the study. A total of 2 plasma oxalate profiles and a pre-dialysis plasma oxalate sample need to be collected AFTER the new stable dialysis regimen has been established for at least 4 weeks.

Plasma glycolate assessments should be done twice: once with the initial screening assessments and again on Day 1 prior to dosing. Results of the plasma glycolate assessments are not required prior to dosing.

Figure 1: Minimum Blood Sample Collection for PD Assessments During Screening

Abbreviations: POx=plasma oxalate; PGly=plasma glycolate.

Note, POx Profile Assessment is the area under the curve (AUC) between dialysis sessions; see Table 6 for POx Profile Assessment blood sample time points.

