3.3. Exploratory Endpoints

The following are the exploratory endpoints:

- Growth parameters in patients who are < 6 years of age at consent
- Change in developmental milestones over time in patients < 6 years of age at consent
- Change in QoL as assessed by EQ-5D-Y and PedsQL (individual subscales of the generic and ESRD modules, and ESRD module total score) for patients ≥ 2 to 18 years of age at consent, and as assessed by EQ-5D-5L in patients ≥ 18 years of age at consent
- Change in QoL as assessed by KDQOL Symptoms and Problems of Kidney Disease subscale in patients ≥ 18 years of age at consent
- Change in patient and caregiver resource use (eg, work/school attendance, visits to doctor/hospital)
- Change in patient and caregiver experiences as evaluated by a patient experience questionnaire and a caregiver experience questionnaire
- Frequency of ADA
- Change in urinary and plasma glycolate, where urinary glycolate is measured by urinary glycolate:creatinine ratio

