5.2. General Methods

Continuous data will be described using descriptive statistics such as the number of observations (n), mean, standard deviation, standard error, median, quartiles, minimum, and maximum. For the summary statistics of all numerical variables unless otherwise specified, minimum and maximum will be displayed to the same level of precision as reported. Median and mean will be presented to the level of precision collected in the database plus one additional decimal. The standard deviation and standard error will be presented to the level of precision collected in the database plus 1 additional decimal. For any assessments with repeated collections at a given study visit (eg height) the mean will represent the value at that visit unless otherwise noted. For biomarker and/or lab data, if any value is recorded as <lower limit of detection (LLOD) then the value assigned for calculations will be the LLOD.

Categorical and ordinal data will be described using the patient count and percentages in each category. When count data are presented, the percentage will not be presented when the count is zero.

Summaries of tables and figures for each study period will include all data collected during the corresponding period as defined in Section 4.1.

The per-patient listings will include all data collected during each study period. For per-patient listings of the extension periods, there will be a variable to indicate the period of the data collection (Primary Analysis Period or Extension Period).

Day 1 will be defined as the day of the first dose of lumasiran. Study day is calculated relative to the first dose date of lumasiran for all patients:

If the assessment date is after the date of first lumasiran dose, then the study day will be calculated as:

$$\text{Study Day} = \text{Date of assessment} - \text{date of first dose of lumasiran} + 1,$$

If the assessment date is before the date of the first dose of lumasiran, then the study day will be calculated as:

$$\text{Study Day} = \text{Date of assessment} - \text{date of first dose of lumasiran}$$

Summary statistics will be presented, as well as 2-sided 95% confidence interval (CI)s for primary/secondary endpoints or selected parameters, as described in the sections below.

All data recorded on the CRF will be displayed in data listings.

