5.4. Baseline Definitions

In Cohort A patients, the plasma oxalate baseline is defined as the mean of all plasma oxalate level values collected prior to the first dose of lumasiran. In Cohort B patients, the plasma oxalate baseline is similarly defined except that the values obtained from the plasma oxalate profile assessment visits will only include the first pre-dialysis sample collected per visit.

For all patients who are not anuric (anuria is defined as <100 ml of urine per day), single-void urine samples (in triplicate) will be collected during screening, with the mean of values for the various parameters measured in these single-void samples used to establish baseline. In these patients, three 24-hour collections will be performed during Screening, with the median values of all the valid samples used to establish baseline urinary oxalate levels.

A 24-hour urine collection will be considered valid if each of the following criteria are met:

- The collection is between 18 to 26 hours in duration between the initial discarded void and the last void or attempt to void.
- No voids are missed between the start and end time of the collection.
- In patients not undergoing dialysis, the 24-hour creatinine content is at least 5 mg/kg for patients <6 years of age, and 10 mg/kg for patients ≥6 years of age as measured in the study central laboratory.

In patients undergoing dialysis, 24-hour collections are not required to have a minimum creatinine content to be considered valid.

Urine data collected from patients that are anuric is considered unreliable; thus there will be no analyses performed for patients that were anuric, from whom urine samples are not collected.

In Cohort B, baseline plasma oxalate AUC measurements will be obtained via the plasma oxalate profile assessments prior to the first dose of lumasiran. Plasma oxalate profile assessments will be performed during Screening, with the mean value of all valid AUC profiles (see Section 7.3.1) being computed to establish the baseline AUC.

For other parameters, baseline is defined as the last non-missing value prior to the first dose date/time of lumasiran, unless otherwise specified. The baseline value for any measurements with multiple values at a visit (eg labs, etc.) will be defined as the mean of all values collected on the most recent date of assessment prior to the first dose date/time of lumasiran.

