7.4.7. Percent and Absolute Change from Baseline in Urinary and Plasma Glycolate

The percent and absolute change from baseline in plasma glycolate and spot urinary glycolate: creatinine ratio will each be summarized at each scheduled assessment.

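### Plasma glycolate is sampled twice before dosing, but the SAP baseline is the Day 1 value alone, which adds noise and an upward bias to the mean percent change of this exploratory endpoint

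*Protocol*

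**What the plan says.** Protocol 6.1 (Screening Assessments) sets two pre-dose samples: "Plasma glycolate assessments should be done twice: once with the initial screening assessments and again on Day 1 prior to dosing". It adds that the results need not be known before dosing, and it does not say how the two values are to be combined.

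SAP 5.4 (Baseline Definitions) gives named rules to four kinds of measurement:
- plasma oxalate: "the plasma oxalate baseline is defined as the mean of all plasma oxalate level values collected prior to the first dose of lumasiran", with a pre-dialysis restriction for profile visits in Cohort B;
- parameters from single-void urine: mean of the screening samples;
- 24-hour urinary oxalate: median of the valid collections;
- plasma oxalate AUC: mean of the valid screening profiles.

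Plasma glycolate is not named, so the default governs: "For other parameters, baseline is defined as the last non-missing value prior to the first dose date/time of lumasiran, unless otherwise specified". Where a measurement has several values, SAP 5.4 takes "the mean of all values collected on the most recent date of assessment". SAP 5.2 adds: "For any assessments with repeated collections at a given study visit (eg height) the mean will represent the value at that visit". Screening and Day 1 are different dates and different visits, so neither rule joins them.

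SAP 3.3 lists the exploratory endpoint as "Change in urinary and plasma glycolate, where urinary glycolate is measured by urinary glycolate:creatinine ratio". SAP 7.4.7 gives the analysis: "The percent and absolute change from baseline in plasma glycolate and spot urinary glycolate: creatinine ratio will each be summarized at each scheduled assessment". It sets no baseline of its own. SAP 8 (Changes to Planned Analyses) does not mention the point.

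**The concern.** Protocol 1.5 describes increased plasma and urinary glycolate as a result of glycolate oxidase inhibition, so this endpoint shows whether the drug hits its target. In anuric patients, for whom SAP 5.4 plans no urine analyses, plasma glycolate is the only such measure.

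Two features suggest an oversight. SAP 7.4.7 handles plasma and spot urinary glycolate in one sentence, yet the urinary ratio gets a mean of three voids as baseline and the plasma value gets one sample. And the screening sample has no stated eligibility or safety use, although blood volume is capped in children.

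The Day 1 value is the denominator of the percent change at every visit. An error in it carries through a patient's whole series, and because the reciprocal is convex, the errors do not cancel in the mean.

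**Working it through.** The documents state no glycolate variability and no expected rise, so there is no planned figure to reproduce. R and CV below are assumptions, shown over a range.

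**Inputs from the documents.** Two pre-dose samples (protocol 6.1). Baseline is the last pre-dose value (SAP 5.4). Exploratory summaries are mean, standard error, median, minimum and maximum, with no test (SAP 7.4). Planned enrolment is 20, with at least 6 per cohort (protocol 7.1, SAP 5.1).

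**Bias.** Percent change is 100 × (Y/B − 1). With independent error of the same CV in every sample and a baseline averaged over k values, E[Y/B] ≈ R(1 + CV²/k). The bias in the mean is therefore about 100 × R × CV²/k points. At R = 5 and CV 0.30:
- k = 1: 100 × 5 × 0.09 = +45 points
- k = 2: 45/2 = +22.5 points

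**Simulation** (2 million draws, lognormal error, R = 5, true change +400%, same true rise in every patient):

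| CV | Bias, one value | Bias, mean of two | SD, one | SD, two | SD reduction |
|---|---|---|---|---|---|
| 10% | +5 | +2.5 | 71.5 | 61.6 | 14% |
| 20% | +20 | +10 | 149 | 126 | 15% |
| 30% | +45 | +22.5 | 236 | 195 | 18% |
| 40% | +80 | +39 | 341 | 271 | 21% |
| 50% | +125 | +62 | 470 | 357 | 24% |

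The bias scales with R. At CV 30% it is +27 against +13 points for R = 3, and +90 against +45 for R = 10.

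**Between-patient variation.** Let the true fold-rise vary with an assumed SD of 2 around a mean of 5, so that E[R²] = 25 + 4 = 29. At CV 30%:
- One value: √(29 × 1.09⁴ − (5 × 1.09)²) = √(40.94 − 29.70) = 3.35, an SD of 335 points.
- Mean of two: from the table case, the mean square per unit R² is (1.949² + 5.225²)/25 = 1.244. Then √(29 × 1.244 − 5.225²) = √(36.08 − 27.30) = 2.96, an SD of 296 points.
- Reduction: 39/335 = 12%.

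The same calculation gives 434 against 363 (about 16%) at CV 40%, and 262 against 245 (about 7%) at CV 20%. So 12–21% describes CV 30–40% with or without this spread. At lower CV with real between-patient spread the gain is smaller.

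**Standard error.** With n = 6, CV 30% and R = 5, the measurement-error part of the SE is 236.5/√6 = 96.5 points with one value and 194.9/√6 = 79.6 with two. The difference in bias, about 22.5 points, is roughly a quarter of that SE (22.5/96.5 = 0.23).

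**Other summaries.** Absolute change has no such bias. The ratio of its SD with one value to that with two is √((R² + 1)/(R² + 0.5)): 1.026, 1.010 and 1.002 for R = 3, 5 and 10. The median percent change is unbiased with one value. With an arithmetic mean of two it falls slightly, by about 10 points on 400 at CV 30% and R = 5.

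**The case against.** The strongest case against runs as follows. The SAP rule is explicit, pre-specified and conventional. For oxalate, protocol 3.1 says the repeated samples are meant to give a robust baseline; it says nothing of the kind for glycolate. The default also favours the most recent state: the screening value may be up to 120 days old, Cohort A renal function may be falling, and a Cohort B dialysis regimen may change during screening. Absolute change and the median are reported alongside the mean.

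Much of this stands. A reader might infer that the SAP contradicts the protocol; it does not, because the protocol never says the two values are to be averaged. A reader might infer that the screening sample is wasted; it is not, because it is the fallback when Day 1 is missing and it appears in the listings. With blood-volume limits, SAP 5.5 expects missing blood tests. A reader might infer that the evidence of target engagement is materially overstated; the documents give no variability or rise from which to show that, and +445% and +422% would support the same conclusion.

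The age of the screening sample is a weaker argument. The SAP accepts the same screening window when it averages every pre-dose plasma oxalate value. The dialysis-change argument calls for an exception in the new rule rather than for leaving the replicate out. Figure 1, which sets the screening glycolate timing, is not shown. If the first Cohort B sample was not taken pre-dialysis, the proposed rule would exclude it and change nothing for that patient.

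**Conclusion.** The point holds as a minor refinement. Under SAP 5.4 the plasma glycolate baseline is a single Day 1 value although a second pre-dose value is collected, and this differs without explanation from the averaged baselines for plasma oxalate and spot urinary glycolate:creatinine.

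The effect is confined to the mean percent change and its spread. Averaging halves the upward bias but does not remove it; a summary on the log-ratio scale would. The sizes rest on the assumed R and CV, on independent errors of equal CV, and on no drift between screening and Day 1. No inference about the primary or secondary endpoints follows.

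**What to change.** Add to SAP 5.4: for plasma glycolate, baseline is the mean of all values collected before the first dose (pre-dialysis values in Cohort B). Where a Cohort B patient's dialysis regimen is permanently changed during screening, leave out samples collected before the new regimen is established, as protocol 6.1 does for plasma oxalate.

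The cost is one SAP sentence with one exception, and no new data. The small downsides are that an older screening value enters the baseline and that the median percent change shifts down slightly. Before the text is final, confirm from Figure 1 or the Laboratory Manual whether the Cohort B screening glycolate sample is taken pre-dialysis.
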